4.10.4.5. Thrombocytopenia TEAE

The number and percentage of patients experiencing events as well as the number of reported events, classified by PT, will be tabulated by treatment group. The risk different (95% CI) in the crude incidence rates between each active treatment group (or total olezarsen) and pooled placebo group will be provided.

• Thrombocytopenia TEAE (defined based on the 'Thrombocytopenias' High Level Terms [HLT] or 'Platelet count decreased' PT)

4.10.4.6. Hypersensitivity TEAE

Hypersensitivity TEAEs will be analyzed for the following categories. The number and percentage of patients experiencing events will be tabulated by treatment group. The risk difference (and 95% CI) in the crude incidence rates between each active treatment group (or total ISIS 678354) and pooled placebo group will also be provided.

- Hypersensitivity TEAE (defined based on the Hypersensitivity SMQ [narrow scope only]) by SOC and PT
- TEAEs in the Hypersensitivity FMQ (narrow) by PT
- Serious TEAEs, fatal TEAEs and TEAEs leading to treatment discontinuation in the Hypersensitivity FMQ (narrow) by PT
- Action taken with drug due to TEAEs in the Hypersensitivity FMQ (narrow)
- Rescue medication used in management TEAEs in the Hypersensitivity FMQ (narrow)
- TEAEs in the Hypersensitivity FMQ (broad) by PT
- Serious TEAEs, fatal TEAEs and TEAEs leading to treatment discontinuation in Hypersensitivity FMQ (broad) by PT
- Action taken with drug due to TEAEs in the Hypersensitivity FMQ (broad)
- Rescue medication used in management TEAEs in Hypersensitivity FMQ (broad)
- TEAEs in the Hypersensitivity algorithmic FMQ. The FMQ definition is using an algorithmic component of the PTs identified within the Hypersensitivity FMQ based on the locations that hypersensitivity is known to commonly affect, i.e., airway, skin, soft tissue, and systemic. In addition, the onset of event(s) is within 7 days of the treatment.
- TEAEs in the Anaphylactic reaction FMQ (narrow) by PT
- Serious TEAEs, fatal TEAEs and TEAEs leading to treatment discontinuation in Anaphylactic reaction FMQ (narrow) by PT

For patients who had hypersensitivity reactions, either in FMQ narrow, broad, or algorithmic, the time to onset of the first event will be summarized using descriptive statistics

For patients who had serious hypersensitivity reactions or discontinued study drug due to hypersensitivity reactions, either in FMQ narrow, broad, or algorithmic, a graphical patient profile will be provided.

4.10.4.7. Renal Impairment TEAE

Renal impairment TEAEs will be analyzed for the following categories. The number and percentage of patients experiencing events will be provided. The risk different (95% CI) in the crude incidence rates between each active treatment group (or total ISIS 678354) and pooled placebo group will be provided.

- Renal impairment TEAEs (defined based on the 'Acute renal failure' SMQ (narrow and broad))
- TEAEs, serious TEAEs, fatal TEAEs, and TEAEs leading to treatment discontinuation in the AKI FMQ (narrow) by PT
- TEAEs, serious TEAEs, fatal TEAEs, and TEAEs leading to treatment discontinuation in the AKI FMQ (broad) by PT

For patients who had treatment emergent proteinuria (defined as all events fall under proteinuria SMQ narrow and broad), the time to onset of the first event will be summarized using descriptive statistics.

For patients who had treatment emergent albuminuria (defined as all related events fall under proteinuria SMQ narrow, including diagnosis tests for albumin/creatinine ratio), the time to onset of the first event will be summarized using descriptive statistics.

For patients who had AKI TEAE (FMQ narrow or broad), the time to onset of the first event will be summarized using descriptive statistics.

For patients who had serious AKI TEAE (FMQ narrow or broad), or discontinued study drug due to AKI TEAE (FMQ narrow or broad), a data listing including eGFR and serum creatinine and a graphical patient profile will be provided.

4.10.4.8. Abnormal Liver Function TEAE

Abnormal liver function TEAEs will be analyzed for the following categories. The number and percentage of patients experiencing events tabulated by treatment group. The risk difference (95% CI) in the crude incidence rates between each active treatment group (or total ISIS 678354) and pooled placebo group will be provided.

- Abnormal liver function TEAE (defined based on the 'Drug related hepatic disorders comprehensive search' SMQ (narrow and broad))
- TEAEs, Serious TEAEs, drug-related TEAEs, fatal TEAEs and TEAEs leading to treatment discontinuation in Hepatic Injury and Hepatic Failure FMQ (narrow)
- TEAEs in Hepatic Injury and Hepatic Failure FMQs (narrow) by PT
- Discontinuations and Lost to follow-up with Liver Safety Lab Elevation or AEs (in Hepatic FMQs)

4.10.5. Clinical Laboratory Evaluation

The following is the list of safety lab analytes that will be collected throughout the study:

- Chemistry: sodium, potassium, chloride bicarbonate, total protein, albumin, calcium, magnesium, phosphorus, glucose, BUN, creatinine, uric acid, total bilirubin, direct (conjugated) bilirubin, indirect (unconjugated) bilirubin, ALT, AST, ALP, creatine kinase, and GGT.
- Hematology: red blood cells, hemoglobin, hematocrit, MCV, MCH, MCHC, RDW, platelets, white blood cells (WBCs), and WBC differential in both percentage and absolute count (neutrophils, eosinophils, basophils, lymphocytes, and monocytes)
- Coagulation: aPTT, PT, international normalized ratio (INR)
- Other assessments: hs-CRP (inflammatory), HOMA-IR, fructosamine, glycated hemoglobin (HbA_{1c}), glycated albumin
- Screening Tests: hepatitis B surface antigen, hepatitis C antibody, HIV antibody, FSH (women), serum βhCG (women). The screening test data will only be displayed in patient listings

• Urinalysis: color, appearance, specific gravity, pH, protein, blood, ketones, urobilinogen, glucose, bilirubin, leukocytes esterase, nitrate, and microscopic examination. The expanded urinalysis data will be only displayed in patient listings. Urine albumin/creatinine ratio (UACR) and protein/creatinine ratio (UPCR) will be summarized.

All safety lab data will also be displayed in patient listings based on all randomized patients. Chemistry, hematology, coagulation, other assessments, selected urinalysis, and selected lipid parameters including LDL-C and apoB (result, change and percent change from Baseline) will be summarized using descriptive statistics (n, mean, standard error, standard deviation, median, Q1, Q3, minimum and maximum) by treatment group and study visit.

A frequency bar chart of the missing data and existing data at each visit for patients remaining in the trial will be provided for creatinine, BUN, total bilirubin, ALT, AST, ALP, estimated Glomerular Filtration Rate (eGFR), hsCRP, hemoglobin, hematocrit, platelets, white blood cells, UACR, UPCR.

Additional analyses of key safety laboratory data

The following analyses of key safety laboratory data will be provided.

Hepatobility Laboratory Abnormalities:

The number and percent of patients falling in each of the following categories based on results after first dose will be tabulated by treatment group. The risk different (95% CI) in the crude incidence rates between each active treatment group (or total ISIS 678354) and pooled placebo group will be provided for selected categories.

- ALT or AST \geq ULN
- The higher of ALT/AST \ge 3 × upper limit of normal (ULN) or ALT/AST \ge 2 × Baseline (i.e., ALT/AST \ge 3 × ULN and ALT/AST \ge 2 × Baseline)
- ALT/AST \geq 3 × ULN
- ALT/AST \geq 5 × ULN
- ALT/AST $\geq 8 \times ULN$
- $ALT/AST \ge 10 \times ULN$
- ALT/AST $\geq 20 \times ULN$
- Highest ALT falling in: ≥ 3 × ULN < 5 × ULN, ≥ 5 × ULN < 10 × ULN, ≥ 10 × ULN -< 20 × ULN (the risk difference will not be provided for this category)
- Total bilirubin $\geq 2 \times ULN$
- Total bilirubin $\geq 5 \times ULN$
- Total bilirubin $\ge 8 \times ULN$
- ALT or AST \geq 3 × ULN and Total bilirubin \geq 2 × ULN
- $ALP \ge 2 \times ULN$ and (baseline $ALP < 2 \times ULN$ or baseline ALP missing)
- Direct bilirubin $\ge 2 \times ULN$
- Direct bilirubin $\geq 5 \times ULN$

- GGT $\ge 2 \times ULN$
- ALT \geq 3 × ULN and INR \geq 1.5
- $ALP \ge 2 \times ULN$
- ALP \geq 3× ULN
- INR $\geq 1.5 \times ULN$
- INR \geq 3 × ULN
- INR \geq 5 × ULN

The number and percent of patients falling in each of the following categories based on confirmed results after first dose will be tabulated by treatment group (a confirmed value is based on a consecutive lab value performed on a different day to, but within 10 days of, the initial value. If that value is in the same or worse category then the initial value is confirmed. If the consecutive value is in a better category then the initial value is confirmed using the consecutive value category. If there is no retest within 10 days then the initial value is presumed confirmed. If there are multiple results on the same day, then the worst value will be utilized in the analysis):

- The higher of ALT/AST \ge 3 × ULN or ALT/AST \ge 2 × Baseline, which is confirmed
- ALT/AST \geq 3 × ULN, which is confirmed
- ALT/AST \geq 5 × ULN, which is confirmed
- ALT/AST $\geq 10 \times$ ULN, which is confirmed
- ALT/AST $\geq 20 \times$ ULN, which is confirmed

For patients having at least 3-fold or greater elevations above the ULN for ALT or AST or for patients with baseline ALT or AST \geq ULN at least 2-fold increases from Baseline, spaghetti plots and a listing of all of the ALT, AST, total bilirubin, direct bilirubin, INR, and ALP records will be provided.

For patients having elevation in liver enzymes (ALT \ge 3 × ULN), the time to onset of the first event will be summarized using descriptive statistics

Other liver abnormalities including elevation of ALT ($\ge 3 \times ULN$) accompanied by INR ≥ 1.5 , elevation of ALT ($\ge 3 \times ULN$) accompanied by elevated total bilirubin $\ge 2 \times ULN$ and ALP $\ge 2 \times ULN$ will be reviewed by the study team and summarized if needed.

Additionally, evaluation of Drug Induced Serious Hepatoxicity (eDISH) plots by treatment group will be provided for liver safety parameters (AST, ALT, Total bilirubin and ALP).

Renal Laboratory Abnormalities:

The number and percent of patients falling in each of the following categories based on results at a) any time after first dose) and b) the final visit will be tabulated by treatment group. The risk different (95% CI) in the crude incidence rates between each active treatment group (or total ISIS 678354) and pooled placebo group will be provided.

- Serum creatinine $\geq 0.3 \text{ mg/dL}$ higher than baseline
- Serum creatinine $\geq 50\%$ higher than baseline

ISIS 678354-CS3

Statistical Analysis Plan

A listing of the creatinine values over time will be provided for each patient meeting either of the two criteria.

The number and percent of patients falling in each of the following additional categories based on results at any time after first dose will also be tabulated by treatment group. The risk different (95% CI) in the crude incidence rates between each active treatment group (or total ISIS 678354) and pooled placebo group will be provided.

- Serum creatinine $\geq 2.0 \times$ baseline, and $\geq 3.0 \times$ baseline
- eGFR reduction from baseline, $\geq 25\%$, $\geq 30\%$, $\geq 50\%$, and $\geq 75\%$
- UACR $\ge 300 \text{ mg/g}$, $\ge 500 \text{ mg/g}$, $\ge 600 \text{ mg/g}$, $\ge 1200 \text{ mg/g}$
- UACR increase from Baseline $\geq 50\%$
- UPCR \geq 500mg/g, \geq 1000 mg/g, \geq 2000 mg/g

A listing of creatinine and eGFR will be provided for those patients having \geq 2-fold elevation above baseline in creatinine or \geq 50% decrease from baseline in eGFR.

For patients having eGFR \geq 25% decrease from baseline, the time to onset of the first event will be summarized using descriptive statistics.

Platelet Abnormalities:

The incidence of patients with post-baseline platelets results falling in each of the following categories will be summarized for the Safety Set and the subset of patients with normal baseline ($\geq 140,000/\text{mm}^3$). The risk different (95% CI) in the crude incidence rates between each active treatment group (or total ISIS 678354) and pooled placebo group will be provided for selected categories.

- Any 2 occurrences of platelet count < 140,000/mm³
- Any single occurrence of platelet count < 100,000/mm³
- Any 2 occurrences of platelet count < 140,000/mm³ or any single occurrence of platelet count < 100,000/mm³
- Worst platelet count falling in: ≥ 140,000/mm³, 100,000/mm³ to < 140,000/mm³, 75,000 to < 100,000/mm³, 50,000 to < 75,000/mm³, 25,000 to < 50,000/mm³, 0 to < 25,000/mm³ (the risk difference will not be provided for this category)
- Worst platelet reduction from Baseline $\geq 30\%$ and $\geq 50\%$

The incidence of patients with post-baseline platelets results falling in each of the following categories based on confirmed results will also be summarized:

- Worst platelet count falling in: ≥ 140,000/mm³, 100,000/mm³ to < 140,000/mm³, 75,000 to < 100,000/mm³, 50,000 to < 75,000/mm³, 25,000 to < 50,000/mm³, 0 to < 25,000/mm³ (the risk difference will not be provided for this category)
- Worst platelet reduction from Baseline $\ge 30\%$ and $\ge 50\%$

For patients having post-baseline platelet count $< 100,000/\text{mm}^3$, the time to onset of the first event will be summarized using descriptive statistics

ISIS 678354-CS3

The correlation between anti-platelet antibodies and platelet decrease as well as immunogenicity status may be explored if supported by data.

Hypersensitivity Related Analyte Abnormalities:

The number and percentage of patients falling in each abnormality category outlined below will be tabulated by treatment group. The risk different (95% CI) in the crude incidence rates between each active treatment group (or total ISIS 678354) and pooled placebo group will be provided for selected categories.

- Eosinophils > 650 cells/uL, > 1500 cells/uL, > 5000 cells/uL
- WBC > 10,800 cells/uL, > 13,000 cells/uL, > 15,000 cells/uL

Shift Analysis

The following hematology and hepatic enzymes lab results will be categorized based on Guidance for Industry – Toxicity Grading Scale for Healthy Adult and Adolescent Volunteers Enrolled in Preventive Vaccine Clinical Trials (September 2007) and the incidence of shift from Baseline to worst post-baseline value taken after the first dose will be summarized. If a patient is missing a baseline value but has a post-baseline value, then the baseline assessment will be labelled as "unknown". Likewise, if a patient has a baseline value but has no post-baseline values, then the worst value will be labelled as "unknown". Number and proportion of patients with shift from baseline to worst post-baseline values based on the confirmed results by toxicity category for ALT, AST, and platelets will also be tabulated.

- Hemoglobin: shift from Baseline to minimum post-baseline value
- WBCs: shift from Baseline to minimum post-baseline value
- WBCs: shift from Baseline to maximum post-baseline value
- Platelets: shift from Baseline to minimum post-baseline value
- Creatinine: shift from Baseline to maximum post-baseline value
- BUN: shift from Baseline to maximum post-baseline value
- ALT: shift from Baseline to maximum post-baseline value
- AST: shift from Baseline to maximum post-baseline value

Hemoglobin change from baseline to minimum post-baseline value will be summarized by toxicity category as well.

Shift from Baseline to maximum post-baseline value for urinary albumin/creatinine ratio, protein/creatinine ratio and LDL-C by treatment group will be provided. The categories for the shift table will be:

- Urinary albumin/creatinine ratio: < 30 mg/g; 30 to < 300 mg/g; $\ge 300 \text{ mg/g}$
- Urinary protein/creatinine ratio: < 150 mg/g; 150 to < 500 mg/g; 500 to < 1000 mg/g; \geq 1000 mg/g
- LDL-C: < 70 mg/dL, 70 to < 100 mg/dL, 100 to < 130 mg/dL, 130 to < 160 mg/dL, 160 to < 190 mg/dL and ≥ 190 mg/dL.

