 - * Abstinence is only acceptable as true abstinence, i.e., when this is in line with the preferred and usual lifestyle of the patient. Periodic abstinence (e.g., calendar, ovulation, symptothermal, post-ovulation methods), declaration of abstinence for the duration of a trial and withdrawal are not acceptable methods of contraception
- 9. Atypical antipsychotic medications (e.g., olanzapine and clozapine) will be allowed if on a stable dose for at least 3 months prior to Screening and dose and regimen expected to remain constant through the end of their participation in this study
- 10. The following concomitant medications will be allowed if on a stable dose for at least 4 weeks prior to Screening and dose and regimen expected to remain constant through the end of their participation in this study (occasional or intermittent use of over-the-counter [OTC] medications will be allowed at Investigator's discretion):
 - a. Statins, omega-3 fatty acids (prescription and OTC), fibrates, or other lipid-lowering medications. Patients taking OTC omega-3 fatty acids should make every effort to remain on the same brand through the end of the study
 - b. Antidiabetic medications

- c. Antihypertensive medications
- d. Oral anticoagulants (e.g., warfarin, dabigatran, rivaroxaban, and apixaban) and regular clinical monitoring is performed
- e. Tamoxifen, estrogens or progestins

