5.2. Exclusion Criteria

- 1. Clinically significant abnormalities in medical history (e.g., previous acute coronary syndrome within 6 months of Screening, major surgery within 3 months of Screening) or physical examination
- 2. Active pancreatitis within 4 weeks prior to Screening
- 3. Screening laboratory results as follows, or any other clinically significant abnormalities in screening laboratory values that would render a patient unsuitable for inclusion
 - a. Platelet count < 100K/mm³ at Screening or Qualification. If the platelet count is < 100K/mm³ up to 2 additional tests may be performed to qualify at both Screening and Qualification.
 - b. Alanine aminotransferase (ALT) or aspartate aminotransferase (AST) > 3.0 × upper limit of normal (ULN)
 - c. Total bilirubin > ULN unless due to Gilbert's syndrome
 - d. Estimated GFR < 45 mL/min/1.73 m² [as determined by the CKD-EPI formula for creatinine clearance; (Levey et al. 2009)]
 - e. Urine protein/creatinine ratio (UPCR) ≥ 500 mg/g, or urine albumin/creatinine (UACR) ratio ≥ 300 mg/g
- 4. Uncontrolled arterial hypertension (BP > 160/100 mm Hg)
- 5. History of bleeding diathesis or coagulopathy or clinically significant abnormality in coagulation parameters at Screening
- 6. Active infection requiring systemic antiviral or antimicrobial therapy that will not be completed prior to Study Day 1 or active Covid-19 infection with or without therapy that will not be resolved by Study Day 1
- 7. Active infection with human immunodeficiency virus (HIV), hepatitis C or hepatitis B diagnosed by initial serological testing and confirmed with RNA testing, or prior treatment for hepatitis C. Patients at Screening who test positive by serology, but negative by RNA may be allowed in consultation with the Sponsor Medical Monitor
- 8. Malignancy within 5 years, except for basal or squamous cell carcinoma of the skin or carcinoma *in situ* of the cervix that has been successfully treated. Patients with a history of other malignancies that have been treated with curative intent and which have no recurrence within 5 years may also be eligible if approved by the Sponsor Medical Monitor
- 9. Blood donation of 50 to 499 mL within 30 days of Screening or of > 499 mL within 60 days of Screening

- 10. Treatment with another investigational drug (non-oligonucleotide), biological agent, or device within 1 month of Screening, or 5 half-lives of investigational agent, whichever is longer

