APPENDIX D. GRADING SCALE FOR ADVERSE EVENTS RELATING TO LABORATORY ABNORMALITIES

Appendix D Grading Scale for Adverse Events Relating to Laboratory Abnormalities

The following grading recommendations for AEs relating to lab test abnormalities are based upon the (CTCAE) Version 5.0, November 2017 with modifications outlined in the footnotes below.

Adverse Event	Mild	Moderate	Severe			
		Hematology	•			
aPTT prolonged	>ULN - 1.5 x ULN	>1.5 - 2.5 x ULN	>2.5 x ULN; bleeding			
Eosinophils increased'	>ULN and >Baseline	578	Steroids Initiated			
Fibrinogen decreased	<1.0 - 0.75 x LLN; if abnormal, <25% decrease from baseline	<0.75 - 0.5 x LLN; if abnormal, 25 - <50% decrease from baseline	<0.5 x LLN; if abnormal, ≥50% decrease from baseline			
Hemoglobin decreased (Anemia)	Hemoglobin (Hgb) <lln -="" 10.0="" dl;
<lln -="" 100="" 6.2="" <lln="" g="" l<="" mmovl;="" td="">Hgb <10.0 - 8.0 g/dL; <6.2 - 4.9 mmol/L; <100 - 80g/L	Hgb <8.0 g/dL; <4.9 mmol/L; <80 g/L; transfusion indicated	</lln></lln>	Hgb <10.0 - 8.0 g/dL; <6.2 - 4.9 mmol/L; <100 - 80g/L	Hgb <8.0 g/dL; <4.9 mmol/L; <80 g/L; transfusion indicated			
Hemoglobin increased**	Increase in >0 - 2 g/dL above ULN or above baseline if baseline is above ULN	Increase in >2 - 4 g/dL above ULN or above baseline if baseline is above ULN	Increase in >4 g/dL above ULN or above baseline if baseline is above ULN			
INR increased	>1.2 - 1.5; >1 - 1.5 times above baseline if on anticoagulation	>1.5 - 2.5; >1.5 - 2.5 x baseline if on anticoagulation; monitoring only indicated	>2.5; >2.5 x baseline if on anticoagulation; dose adjustment indicated			
Lymphocyte count decreased	<lln -="" 800="" mm3; <lln -="" 0.8="" 109/L</lln></lln>	<800 - 500/mm³; <0.8 - 0.5 x 10 ⁹ /L	<500 /mm³; <0.5 x 10 ⁹ /L			
Lymphocyte count increased		>4000/mm ³ - 20,000/mm ³	>20,000/mm ³			
Neutrophil count decreased	<lln -="" 1500="" mm3; <lln -="" 1.5="" 109 /L</lln></lln>	<1500 - 1000/mm ³ ; <1.5 - 1.0 x 10 ⁹ /L	<1000/mm ³ ; <1.0 x 10 ⁹ /L			
Platelet count decreased	<lln -="" 75,000="" mm3; <lln -="" 109 /L</lln></lln>	<75,000 - 50,000/mm ³ ; <75.0 - 50.0 × 10 ⁹ /L	<50,000/mm ³ ; <50.0 x 10 ⁹ /L			
White blood cell decreased	<lln -="" 3000="" mm3; <lln -="" 109 /L</lln></lln>	<3000 - 2000/mm ³ ; <3.0 - 2.0 × 10 ⁹ /L	<2000/mm ³ ; <2.0 x 10 ⁹ /L			
		Chemistry	•			
Acidosis	pH <normal, but="">=7.3</normal,>	-	pH <7.3			

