Alanine aminotransferase increased	>ULN - 3.0 x ULN if baseline normal 1.5 - 3.0 x baseline if baseline abnormal	>3.0 - 5.0 x ULN if baseline normal >3.0 - 5.0 x baseline if baseline abnormal	>5.0 x ULN if baseline normal >5.0 x baseline if baseline abnormal			
Alkaline phosphatase increased	>ULN - 2.5 x ULN if baseline normal 2.0 - 2.5 x baseline if baseline abnormal	>2.5 - 5.0 x ULN if baseline normal >2.5 - 5.0 x baseline if baseline abnormal	>5.0 x ULN if baseline normal >5.0 x baseline if baseline was abnormal			
Alkalosis	pH >normal, but ≤7.5		pH >7.5			
Aspartate aminotransferase increased	>ULN - 3.0 x ULN if baseline normal 1.5 - 3.0 x baseline if baseline abnormal	>3.0 - 5.0 x ULN if baseline normal >3.0 - 5.0 x baseline if baseline abnormal	>5.0 x ULN if baseline normal >5.0 x baseline if baseline abnormal			
Blood bilirubin increased	>ULN - 1.5 x ULN if baseline normal >1.0 - 1.5 x baseline if baseline abnormal	>1.5 - 3.0 x ULN if baseline normal >1.5 - 3.0 x baseline if baseline abnormal	>3.0 x ULN if baseline normal >3.0 x baseline if baseline abnormal			
Cardiac troponin I increased	Levels above the upper limit of normal and below the level of myocardial infarction as defined by the manufacturer	-	Levels consistent with myocardial infarction as defined by the manufacturer			

Adverse Event	Mild	Moderate	Severe				
Cardiac troponin T increased	Levels above the upper limit of normal and below the level of myocardial infarction as defined by the manufacturer	-	Levels consistent with myocardial infarction as defined by the manufacturer				
CD4 lymphocytes decreased	<lln -="" 500="" mm3; <lln -="" 0.5="" 109 /L</lln></lln>	<500 - 200/mm³; <0.5 - 0.2 × 10 ⁹ /L	<200/mm ³ ; <0.2 x 10 ⁹ /L				
CPK increased*	>ULN - <6 ULN	6 - 10 x ULN	>10 x ULN				
Creatinine increased**	>ULN - 1.5 x ULN if baseline normal > 1.0 - 1.5 x baseline if baseline abnormal	>1.5 - 3.0 x ULN if baseline normal >1.5 - 3.0 x baseline if baseline abnormal	>3.0 x ULN if baseline normal >3.0 x baseline if baseline abnormal				
GGT increased	>ULN - 2.5 x ULN if baseline normal 2.0 - 2.5 x baseline if baseline abnormal	>2.5 - 5.0 x ULN if baseline normal >2.5 - 5.0 x baseline if baseline abnormal	>5.0 x ULN if baseline normal >5.0 x baseline if baseline abnormal				

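### The bilirubin and INR rows of the liver-abnormality tables carry no baseline condition, so a Gilbert's or warfarin patient can be counted on a pre-existing value

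*Combined protocol and SAP*

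**What the plan says.** The hepatobiliary part of SAP 4.10.5 counts patients by category "based on results after first dose will be tabulated by treatment group". The rows at issue are:

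- total bilirubin at or above 2, 5 and 8 x ULN;
- direct bilirubin at or above 2 and 5 x ULN;
- INR at or above 1.5, 3 and 5 x ULN;
- the combined rows "ALT or AST \geq 3 × ULN and Total bilirubin \geq 2 × ULN" and "ALT \geq 3 × ULN and INR \geq 1.5".

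None of them refers to baseline. Two other entries in the same list do. One ALT/AST row also requires at least twice baseline, and one ALP row requires a baseline below 2 x ULN "or baseline ALP missing". ALP at or above 2 x ULN appears a second time without that condition, so the SAP reports it both ways.

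Protocol 5.2, criterion 3c, excludes "Total bilirubin > ULN unless due to Gilbert's syndrome" and sets no upper limit for Gilbert's patients. Protocol 5.1, criterion 10d, allows, on a stable dose, "Oral anticoagulants (e.g., warfarin, dabigatran, rivaroxaban, and apixaban) and regular clinical monitoring is performed". Protocol Appendix D grades INR as mild at ">1 - 1.5 times above baseline if on anticoagulation" and bilirubin as mild at ">1.0 - 1.5 x baseline if baseline abnormal", with the higher grades built the same way.

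**The concern.** Bilirubin and INR are the two liver analytes for which the eligibility criteria foresee a raised value before treatment. Appendix D adjusts for this when grading adverse events; the abnormality tables do not. A patient whose bilirubin or INR was already above a cut-off before the first dose, and merely stays there, appears in the table like a patient who crossed the cut-off on study.

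These rows would normally hold very few patients. With arms of just over twenty, a single such patient could be the whole content of a row, for or against the drug.

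**Working it through.** **Inputs.** Row definitions: SAP 4.10.5. Eligibility: protocol 5.1 and 5.2. Sampling: protocol Appendix A. Baseline: SAP 4.2.2, which for these analytes takes the latest available value before first dose. Arm sizes: 22 (80 mg), 21 (50 mg) and 23 (placebo), from the lay summary of results; the plan of 60 implies 20 per arm (30 x 2/3 active per cohort, 10 + 10 placebo). The plan states no figure on this point, so there is none to reproduce.

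**Step 1: which rows can be met with no change on study?**

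| Row | Can the value pre-date dosing? |
|---|---|
| Total or direct bilirubin alone | Yes. There is no baseline condition, and criterion 3c caps nothing for Gilbert's. |
| INR alone | Yes, if a permitted anticoagulated patient enters above the cut-off. |
| ALT or AST >= 3 x ULN with total bilirubin >= 2 x ULN | Only the bilirubin part. |
| ALT >= 3 x ULN with INR >= 1.5 | Only the INR part. |

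For the combined rows, criterion 3b in protocol 5.2 excludes ALT or AST above 3.0 x ULN at Screening. The transaminase part must therefore arise on study, with two narrow exceptions: a value of exactly 3.0 x ULN, and a rise between Screening and Day 1.

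**Step 2: does another planned table separate old from new values?**

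- The shift tables cover hemoglobin, white cells, platelets, creatinine, BUN, ALT, AST, UACR, UPCR and LDL-C, but not bilirubin or INR.
- The confirmed-result liver tables cover ALT and AST only.
- By-visit change from baseline is summarized for chemistry and coagulation, but that gives no patient counts.
- The full liver listing and spaghetti plots are triggered by ALT or AST, so they reach combined-row cases but not a patient counted only for bilirubin or INR.
- The eDISH plots do not include INR, and nothing says they are adjusted for baseline.

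No planned incidence table makes the distinction.

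**Step 3: is a baseline available?** Appendix A schedules coagulation at Screening, Day 1, Week 25 and Week 53. Bilirubin is in the chemistry panel, which is also taken before dosing. The condition can be derived without new data.

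**Step 4: size.** One patient counted on an old value adds 1/n to that arm: 1/23 = 4.3, 1/22 = 4.5 and 1/21 = 4.8 percentage points; 1/43 = 2.3 for the pooled active arms; 1/20 = 5.0 at the planned size. The Miettinen-Nurminen 95% limits named in SAP 4.10 are the values d that solve (p1 - p2 - d)^2 / V(d) = 3.84, where V is evaluated at the estimates restricted to difference d and multiplied by N/(N - 1):

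| Counts (active vs placebo) | Difference (points) | 95% CI |
|---|---|---|
| 0/22 vs 0/23 | 0.0 | -14.6 to 15.2 |
| 1/22 vs 0/23 | +4.5 | -10.4 to 22.1 |
| 2/22 vs 0/23 | +9.1 | -6.2 to 28.1 |
| 0/22 vs 1/23 | -4.3 | -21.3 to 11.1 |
| 1/43 vs 0/23 | +2.3 | -12.3 to 12.2 |

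**Step 5: how likely is any such patient?** The documents do not say. If a proportion p carried such a baseline value, the chance of at least one among 66 is 1 - (1 - p)^66: 74% at p = 2%, 97% at 5%, and above 99% at 10%. These proportions are assumptions, and zero is possible.

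**The case against.** The case against is substantial.

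- **The combined rows still signal something new.** They need an essentially on-study rise to 3 x ULN, so a reader who inferred that Hy's-law-type rows can fill with pre-existing values would be wrong. This stands.
- **The SAP mirrors the protocol.** The third liver stopping rule in protocol 8.6.1 pairs transaminases with total bilirubin above 2 x ULN or INR above 1.5, with no baseline condition on either. This stands, and is a good reason to keep the existing rows.
- **Case-level review exists.** Listings, plots and study-team review would expose a misclassified combined case. This stands, but exposure does not alter the tabulated count. The review clause is also worded for ALT only and joins its bilirubin case to ALP.
- **The tables are not labelled treatment-emergent.** Adverse events are handled separately, and the definition in SAP 4.10.2 requires worsening of a pre-existing condition. True, but a table of results after first dose, by arm, invites that reading.
- **Conditioning could hide a signal.** If conditioned rows replaced the current ones, a Gilbert's or anticoagulated patient with genuine new liver injury might drop out. This stands and shapes the fix.
- **Exclusion criterion 5 may remove some raised-INR patients.** It covers clinically significant coagulation abnormality at Screening. The documents do not say how it applies to permitted warfarin users.

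**Conclusion.** The point holds for the single-analyte bilirubin and INR rows, which can count a wholly pre-existing value. For the two combined rows it holds only for the bilirubin or INR part. It is a reporting weakness in descriptive safety tables: no hypothesis test depends on it, and every interval in the illustration includes zero.

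The size is 4.3 to 4.8 points per affected patient in arms of 21 to 23, in either direction. That rests on the reported arm sizes and on at least one patient entering at or above a cut-off, which the documents neither confirm nor rule out.

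Three stronger readings are tempting but unsupported. A reader might infer that every count feeds a risk difference; the SAP limits these to selected categories and does not name them. A reader might infer that baseline is considered only for ALP; one ALT/AST row uses it too. A reader might infer that a patient kept on warfarin will probably be flagged; the documents give no INR target or baseline INR values from which to judge that.

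**What to change.** Keep all existing rows unchanged. Beside each bilirubin and INR row and both combined rows, add a parallel row, following the SAP's own treatment of ALP at 2 x ULN. The added row counts a patient if:

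1. the baseline bilirubin or INR was below that row's cut-off, or was missing; or
2. the baseline was already at or above the cut-off and the value worsened relative to baseline on the Appendix D scale.

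For the combined rows, apply the condition to the bilirubin or INR part and leave the transaminase part as it is. State in advance which Appendix D grade counts as worsening, since the mild grade begins just above baseline. Use the SAP 4.2.2 baseline, and list the patients who appear in one row of a pair but not the other.

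The cost is SAP wording, one derived flag and ten extra rows (3 total bilirubin + 2 direct bilirubin + 3 INR + 2 combined). No new data are needed. The downside is a slightly longer table.
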